## 6.7.3 Contraception

AGI-134 effect on foetus in utero was not tested to date.

For this study, male subjects will be of non-reproductive potential, if they have azoospermia (whether due to having had a vasectomy or due to an underlying medical condition).

Males and non-pregnant, non-breastfeeding females may only be enrolled if they are willing to use 2 methods of birth control or are considered highly unlikely to conceive. Highly unlikely to conceive is defined as;

- 1) surgically sterilised
- 2) Women of non-childbearing potential (see definition in section 4.1 Inclusion Criteria)
- 3) not heterosexually active for the duration of the study when this is in line with the preferred and usual lifestyle of the subject.

The two birth control methods can be a barrier method plus a hormonal method to prevent pregnancy. Subjects should start using birth control from Screening visit (or 21 days prior to investigational product administration for oral contraception) and throughout the Core Study up to 120 days after the last dose of study medication.

The following are considered adequate barrier methods of contraception: Diaphragm, condom (by the partner) or sponge; each of which are to be combined with a spermicide or a copper intrauterine device as per local regulations or guidelines. Appropriate hormonal contraceptives will include any registered and marketed contraceptive agent that contains an oestrogenic and/or a progestational agent (including oral, subcutaneous, intrauterine or intramuscular agents).

Subjects should be informed that taking the study medication may involve unknown risks to the foetus (unborn baby) if pregnancy were to occur during the study. In order to participate in the study, subjects of childbearing potential must adhere to the contraception requirement (described above) for the duration of the study and 120 days after the last dose of study treatment. If there is any question that a subject of childbearing potential will not reliably comply with the requirements for contraception, that subject should not be entered into the study.

20		PRIVILEGED & CONFIDENTIAL
Investigational Product: AGI-134	A Phase I/IIa, multicentre, two-parts, open label study designed to evaluate the safety and tolerability of escalating	Protocol No. AGI-134.FIM.101
Phase: I/IIa		Version 6.1 31 May 2021

## 6.7.3.1 Use in Pregnancy

If a subject inadvertently becomes pregnant while on treatment with investigational product, the subject will immediately be removed from the study. The site will contact the subject at least monthly and document the subject's status until the pregnancy has been completed or terminated. The outcome of the pregnancy will be reported to the Sponsor without delay and within 24 hours if the outcome is a serious adverse experience (e.g., death, abortion, congenital anomaly or other disabling or life-threatening complication to the mother or new-born). The Study PI will make every effort to obtain permission to follow the outcome of the pregnancy and report the condition of the foetus or new-born to the Sponsor. If a male subject impregnates his female partner, the site personnel must be informed immediately, and the pregnancy reported to the Sponsor and followed as described above and in Section 7.2.6 Reporting of Pregnancy and Lactation to the Sponsor.

## 6.7.3.2 Use in Nursing Women

Since it is unknown whether AGI-134 is excreted in human milk and due to the potential for serious adverse reactions in the nursing infant, subjects who are breastfeeding are not eligible for enrolment.

#### 6.7.4 Dose Modifications

AGI-134 concentration is fixed. In Part 1, doses will be escalated starting with 25 mg up to 200 mg. Each dose can be injected into one lesion or can be divided to several lesions, depending on the lesion size. When the MTD is reached or the 200 mg dose is found to be safe, whichever comes first, the RP2D will have been determined and the study will continue to Part 2. In Part 2, the dose will be deduced according to the tumour dimensions and up to a maximum dose according to the RP2D.

Interruptions from the protocol-specified treatment more than the allowed below, require consultation between the PI and the Sponsor and written documentation of the collaborative decision on subject management.

Dosing interruptions are permitted in case of medical/surgical events or logistical reasons not related to study therapy (e.g., elective surgery, unrelated medical events, subject vacation, and/or holidays). Subjects should be placed back on study therapy within 3 weeks of the scheduled interruption, unless otherwise discussed with the Sponsor's MM. The reason for interruption should be documented in the subject's study record.

This is a first-in-human study with AGI-134, therefore, no dose modifications are proposed. The dosing of AGI-134 will be explored by an escalation phase followed by the expansion phase. If modifications are needed, they will be explored within this study.

50		PRIVILEGED & CONFIDENTIAL
Investigational Product: AGI-134	A Phase I/IIa, multicentre, two-parts, open label study designed to evaluate the safety and tolerability of escalating	Protocol No. AGI-134.FIM.101
Phase: I/IIa		Version 6.1 31 May 2021

## 6.7.4.1 Rescue Medications & Supportive Care Guidelines for AGI-134

This is a first-in-human study with AGI-134, therefore, no specific guidelines are pre-defined. AE should be treated according to the PI best clinical judgement.

### 7 SAFETY PHARMACOVIGILENCE

#### 7.1 Adverse Events

An AE is defined in the International Conference on Harmonisation (ICH) E6 as "any untoward medical occurrence in a subject or clinical investigation subject administered a pharmaceutical product and which does not necessarily have a causal relationship with this treatment. An AE can therefore be any unfavourable and unintended sign (including an abnormal laboratory finding), symptom or disease temporally associated with the use of a medicinal (investigational) product, whether or not related to the medicinal (investigational) product."

An abnormal result of diagnostic procedures including abnormal laboratory findings will be considered an AE if it fulfils one or more of the following:

- Results in subject's withdrawal by the PI
- Is associated with an SAE
- · Is associated with clinical signs or symptoms
- Is considered by the PI to be of clinical significance

A new condition or the worsening of a pre-existing condition will be considered an AE.

### AEs do not include the following:

- Medical/surgical procedures (e.g., surgery, endoscopy, tooth extraction, transfusion).
   The condition that leads to the procedure is an AE if the procedure was not planned at Screening visit.
- Overdose of concomitant medication without any signs or symptoms unless the subject is hospitalised for observation.
- Hospitalisation for elective surgery planned prior to study (situation where an untoward medical occurrence has not occurred).
- Progression of the cancer under study, unless it is considered to be drug-related by the PI.

agalimmune A subsidiary of BIOLINERX		PRIVILEGED & CONFIDENTIAL
Investigational Product: AGI-134	A Phase I/IIa, multicentre, two-parts, open label study designed to evaluate the safety and tolerability of escalating	Protocol No. AGI-134.FIM.101
Phase: I/IIa	doses of AGI-134 in unresectable/metastatic solid tumours.	Version 6.1 31 May 2021

Once the subject has signed the Informed Consent Form (ICF), AEs will be recorded up to 30 days after the last dose of study drug, or until the initiation of new anti-cancer therapy, whichever sooner. SAEs will be recorded up to 90 days following the last dose of study drug or until the subject initiates new anti-cancer therapy, whichever is sooner. All AEs, whether observed by the PI or designee or volunteered by or elicited from the subject, should be recorded individually on an AE eCRF page with the following information: The specific event or condition, whether the event was present pre-treatment initiation or not, the dates and times (using the 24 hour clock, where midnight is 00:00 and noon is 12:00) of occurrence, duration, severity, relationship to study medication or to the study procedures of drug administration or biopsy, action taken with the investigational product, outcome, and whether considered non-serious or serious, drug-related or not.

The relationship of the adverse event to the study medication should be assessed by the PI or designee and recorded accordingly. Causality will be reported as follows:

- Likely related to the study medication
- · Likely related to the procedure: i.e. study drug injection and/or biopsy
- Likely related to disease under study
- Not related
- Other, if none of the above is applicable

The severity of the AE will be assessed by the PI in accordance with the definitions below. A Serious AE must fulfil the requirements listed in Section 7.2.

AEs severity (Table 4) will be recorded and graded according to the latest version of the NCI-CTCAE (currently version 5.0) and coded into the database according to the latest version of MedDRA (currently version 24.0).

Table 4: Severity of Adverse Events According to CTCAE (Version 5.0)

Grade	Description
0	No AE or within normal limits
1	Mild; asymptomatic or mild symptoms; clinical or diagnostic observations only; intervention not indicated.
2	Moderate; minimal, local or non-invasive intervention indicated; limiting age-appropriate instrumental Activities of Daily Living (ADL)
3	Severe or medically significant but not immediately life-threatening; hospitalisation or prolongation of hospitalisation indicated; disabling; limiting self-care ADL
4	Life-threatening consequences; urgent intervention indicated
5	Death related to AE

A semi-colon indicates 'or' within the description of the grade.

A single dash (-) indicates a grade is not available

The following definitions should be used for toxicities/AEs that are not defined in the CTCAE:

Protocol AGI-134.FIM.101 CONFIDENTIAL Page 65 of 108

20		PRIVILEGED & CONFIDENTIAL
Investigational Product: AGI-134		Protocol No. AGI-134.FIM.101
Phase: I/IIa		Version 6.1 31 May 2021

- Mild (Grade 1): The AE is noticeable to the subject but does not interfere with routine activity, no medical intervention is required;
- Moderate (Grade 2): The AE interferes with routine activity but responds to symptomatic therapy or rest;
- Severe (Grade 3): The AE significantly limits the subject's ability to perform routine activities despite symptomatic therapy;
- Life-threatening (Grade 4): The subject is at immediate risk of death.

The PI will document his opinion of the relationship of the AE to treatment with investigational product using the criteria outlined in Table 5.

Outcome to Date are classified as follows:

- Recovered: The subject has fully recovered from the AE with no observable residual effects
- Recovered with sequelae: The subject has recovered from the AE with observable residual effects
- Improved: The subject status has improved but is not fully recovered
- Ongoing: AE is not recovered
- Fatal
- Unknown

AEs will be coded by Data Management using the latest version of MedDRA (currently version 24.0) AE dictionary.

All AEs, serious and not serious, will be recorded on the AE Case Report Form, and if relevant, the Concomitant Medications Record in the eCRF will be updated. Severity and relationship to investigational product will be assessed by the PI as described in Table 4 and Table 5 respectively. Particular attention should be made to ensure no discrepancies between the AE and the SAE form (i.e., outcome, severity, relationship must be consistent).

Treatment-Emergent Adverse Events (TEAEs) are defined as AEs observed after first dose of investigational product.

agalin A subsidiary of Bio	nnune DLINERX	PRIVILEGED & CONFIDENTIAL
Investigational Product: AGI-134	A Phase I/IIa, multicentre, two-parts, open label study designed to evaluate the safety and tolerability of escalating	Protocol No. AGI-134.FIM.101
Phase: I/IIa		Version 6.1 31 May 2021

Table 5: Relationship of AE to Treatment

Term	Definition	Clarification
No reasonable possibility (not related)	This category applies to AEs which, after careful consideration, are clearly due to extraneous causes (disease, environment, etc) or to AEs, which, after careful medical consideration at the time they are evaluated, are judged to be unrelated to the investigational product.	The relationship of an AE may be considered "no reasonable possibility" if it is clearly due to extraneous causes or if at least 2 of the following apply:  It does not follow a reasonable temporal sequence from the administration of the test drug.  It could readily have been produced by the subject's clinical state, environmental or toxic factors, or other modes of therapy administered to the subject.  It does not follow a known pattern of response to the test drug.  It does not reappear or worsen when the drug is re-administered.
Reasonable possibility (related)	This category applies to AEs for which, after careful medical consideration at the time they are evaluated, a connection with the test drug administration cannot be ruled out with certainty nor felt with a high degree of certainty to be related to the investigational product.	The relationship of an AE may be considered "reasonable possibility" if at least 2 of the following apply:  It follows a reasonable temporal sequence from administration of the drug.  It cannot be reasonably explained by the known characteristics of the subject's clinical state, environmental or toxic factors, or other modes of therapy administered to the subject.  It disappears or decreases on cessation or reduction in dose. There are important exceptions when an AE does not disappear upon discontinuation of the drug, yet drug-relatedness clearly exists.  It follows a known pattern of response to the test drug.

#### 7.2 Serious Adverse Events

An SAE is any AE occurring at any dose that suggests a significant hazard or side effect, regardless of the PI or Sponsor's opinion concerning the relationship to the investigational product and that result in, but may not be limited to, any of the following outcomes:

- Death (regardless of the cause)
- A life-threatening experience
- Inpatient hospitalisation or prolongation of existing hospitalisation (any inpatient hospital admission that includes a minimum of an overnight stay in a health care facility)
- A persistent or significant disability/incapacity
- A congenital anomaly or birth defect in an offspring of a study subject
- Significant medical events that may not result in death, be life-threatening, or require hospitalisation may be **serious** when, based upon appropriate medical judgement, they

Protocol AGI-134.FIM.101 CONFIDENTIAL Page 67 of 108

agalin A subsidiary of BIG	nnune BLINERX	PRIVILEGED & CONFIDENTIAL
Investigational Product: AGI-134		Protocol No. AGI-134.FIM.101
Phase: I/IIa		Version 6.1 31 May 2021

may jeopardise the subject and may require medical or surgical intervention to prevent one of the outcomes listed above.

Inpatient hospitalisation or prolongation of existing hospitalisation means that hospital inpatient admission and/or prolongation of hospital stay were required for treatment of AE, or that they occurred as a consequence of the event.

Hospitalisation for elective treatment of a pre-study condition (pre-treatment initiation) that did not worsen while on study and optional hospitalisations not associated with a clinical AE (e.g. elective cosmetic surgery) are not considered SAEs.

**Significant medical events** are those that may not be immediately life-threatening but may jeopardise the subject and may require intervention to prevent one of the other serious outcomes listed above. Examples of such events are intensive treatment in an emergency room or at home for allergic bronchospasm, blood dyscrasias or convulsions that do not result in hospitalisation. Such an AE will normally be considered serious by this criterion.

Progression of the cancer under study is not considered an AE unless it is considered to be drugrelated by the PI.

In addition to the above criteria, AEs meeting any of the below criteria, although not serious per ICH definition, are reportable to the Sponsor for collection purposes as they are considered serious by Sponsor (in the same timeframe as SAEs, as 'significant medical events' to meet certain local requirements):

- A new cancer (that is not a condition of the study)
- Events associated with an excess dosing of investigational product above the recommended dose/per tumour size or dosing schedule.

Methods for follow-up for these criteria can be found in the Investigator Site File, or equivalent.

A **life-threatening** adverse drug experience is any AE that places the subject, in the view of the PI, at immediate risk of death from the reaction as it occurred, i.e., it does not include a reaction that, had it occurred in a more severe form, might have caused death.

Any newly reported SAE, after Termination/Early Termination Visit, that is considered to be related to the investigational product or study participation, should be recorded and reported immediately to Sponsor or designee.

agalin A subsidiary of BIO		PRIVILEGED & CONFIDENTIAL
Investigational Product: AGI-134	A Phase I/IIa, multicentre, two-parts, open label study designed to evaluate the safety and tolerability of escalating	Protocol No. AGI-134.FIM.101
Phase: I/IIa		Version 6.1 31 May 2021

# 7.2.1 Definition of an Overdose for this Protocol and Reporting of Overdose to the Sponsor

An overdose in AGI-134 in humans cannot be defined as this is a first in human study.

In a GLP repeat-dose toxicology study in Cynomolgus monkeys, AGI-134 was well tolerated at doses exceeding the highest planned clinical dose (200 mg). The NOAEL was considered to be 50 mg/kg/dose (SC) (~5-fold higher than the highest expected clinical dose) and 10 mg/kg/dose (IV) (equivalent to the highest planned clinical dose that covers the highly vascularised nature of some solid tumour types and the risk encountered in the worst case of high systemic exposure).

No specific information is available on the treatment of an overdose of AGI-134. In the event of overdose, the subject should be observed closely for signs of toxicity. Appropriate supportive treatment should be provided if clinically indicated.

Refer to Safety Manual for Reporting of Overdose to Sponsor Instructions

## 7.2.2 Reporting Period of Serious Adverse Event

Once the subject has signed the Informed Consent Form (ICF), SAEs will be recorded up to 90 days following the last dose of study drug or until the subject initiates new anti-cancer therapy, whichever is earlier. All SAEs will be followed up for outcome.

Any SAEs, or follow-up to a SAE should be reported within 24 hours to the Sponsor. This includes death due to any cause other than progression of the cancer under study, whether or not related to the investigational product.

Additionally, any SAE, considered by a qualified physician to be related to the Sponsor's product that is brought to the attention of the PI at any time after the Termination/ET visit and up to 5 years, must also be reported immediately to the Sponsor.

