## Week 18, 27, 36 and 45 Visits Procedures:

- Review of change in concomitant medication
- AE Recordings (AEs up to 30 days post last dose of study drug and SAEs up to 90 days post last dose of study drug)
- Examination of injection site
- ECOG performance status
- Photography pictures of all injected superficial tumour, if applicable.
- Tumour Imaging assessment
- RECISTv.1.1 assessment will be done using imaging and/or superficial lesion measurement according to the tumour type.

agalin A subsidiary of BIO		PRIVILEGED & CONFIDENTIAL
Investigational Product: AGI-134	A Phase I/IIa, multicentre, two-parts, open label study designed to evaluate the safety and tolerability of escalating	Protocol No. AGI-134.FIM.101
Phase: I/IIa	doses of AGI-134 in unresectable/metastatic solid tumours.	Version 6.1 31 May 2021

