## 5.4 Termination or Early Termination Study Visit (Week 54 or ET)

The total study participation period is 54 weeks. Treatment with AGI-134 will be provided for up to 4 cycles (12 weeks). A Termination visit will be performed at Week 54 for all subjects.

In case of Early Termination (ET), all reasons for treatment discontinuation will be documented in the source documents yet only one reason (the most severe) for ET should be recorded in the eCRF. If one of the reasons for early termination is an AE, this should be chosen as the reason. Every effort should be made to follow-up these subjects until resolution or stabilisation of the AE.

At this visit, the following activities will be performed. Exceptions for assessments may be provided in case these assessments were done 1-2 cycles prior to Termination visit and after discussion and approval by the study MM.

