## 5.5 Long-Term Follow-Up

All subjects, including early terminated subjects, will be contacted by phone every 9 weeks (±7 days) after Termination/ET visit (Week 54). This Follow-Up will continue for 5 years. During these phone calls, subjects will be asked to provide an update about disease status and post-study anti-cancer therapy received. During the first Long-Term follow-up visit, subjects should be questioned regarding the occurrence of AEs/SAEs and the outcome of any AEs/SAEs that were ongoing at the Termination/Early Termination visit. However, only AEs that occurred up to 30 days after the last dose of study drug and SAEs that occurred up to 90 days after the last dose of study drug will be recorded in the eCRF (see sections 7.1 and 7.2.2 for details). In case of death, every effort should be done in order to capture the date and reason for death. All the data will be collected and entered within the eCRF.

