#### 7.2.4 Exceptions in the Reporting of SAE

There will be no exceptions in the reporting of SAEs in this study, as this is a first-in-man study.

agalin A subsidiary of Bio	nnune DLINERX	PRIVILEGED & CONFIDENTIAL
Investigational Product: AGI-134		Protocol No. AGI-134.FIM.101
Phase: I/IIa	l l	Version 6.1 31 May 2021

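### Routine SAE recording stops 90 days after the last dose, but the explicit duty for related SAEs starts only after the Termination/ET visit, so for about 31-32 weeks a completer's related SAEs rest on undated general clauses

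*Combined protocol and SAP*

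**What the plan says.** The protocol gives two dated SAE rules.

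**Routine rule.** Section 7.2.2 states: "SAEs will be recorded up to 90 days following the last dose of study drug or until the subject initiates new anti-cancer therapy", whichever comes first. The same limit stands in the synopsis (Ongoing Safety Assessment and Dose-Limiting Toxicity), Sections 3.1.1, 5.8.1, 7.1 and 8.3, and Table 7 footnote 24. The procedure list for the Week 18, 27, 36 and 45 visits repeats it: "AE Recordings (AEs up to 30 days post last dose of study drug and SAEs up to 90 days post last dose of study drug". So does the Termination/Early Termination list in Section 5.4. Section 5.5, on the first long-term follow-up contact, says that only "SAEs that occurred up to 90 days after the last dose of study drug will be recorded in the eCRF".

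**Late rule, related SAEs only.** Section 7.2 covers "Any newly reported SAE, after Termination/Early Termination Visit, that is considered to be related to the investigational product or study participation", which is to be recorded and reported at once. Section 7.2.2 covers a related SAE "brought to the attention of the PI at any time after the Termination/ET visit and up to 5 years, must also be reported immediately". Both start at the Termination/ET visit. Section 5.4 fixes that visit for completers: "A Termination visit will be performed at Week 54 for all subjects".

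**Undated clauses.** Section 7.2.2 also wants any SAE reported to the sponsor within 24 hours. Section 7.2.5.1 wants the initial form within 24 hours of the investigator's knowledge. Section 4.6, on withdrawals, has a similar 24-hour duty. Section 7.2.4 adds: "There will be no exceptions in the reporting of SAEs in this study, as this is a first-in-man study". None of these gives a period.

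**The concern.** The end of one dated rule and the start of the other are tied to different events: the last dose and the Termination visit. For a subject who stays in the Core study these are far apart. During the interval the subject still attends site visits with AE recording on the list, yet the list itself limits SAEs to the 90 days after the last dose. An investigator who follows it would not record a new related SAE disclosed in person at Week 36. The same event first disclosed by telephone after Week 54 would have to be reported immediately. The documents give no reason for a duty that lapses during site follow-up and returns during telephone follow-up.

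At stake is the completeness of the safety data. This is the first study of the product in humans, its primary objective is safety and tolerability, and the product is intended to provoke a systemic immune response. The Safety Committee reviews data every 6 months until the last patient's last visit, and the sponsor's SUSAR reporting depends on what sites send in. Late related events that sites are not clearly told to record may not reach either.

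**Working it through.** The protocol does not state the length of the interval, so there is no figure of its own to reproduce. The check is calendar arithmetic.

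**Inputs**
- Four doses, one every 3 weeks, each on Day 1 of its cycle (Sections 3, 5.3.1 and 5.3.4).
- Routine SAE window: last dose + 90 days (Section 7.2.2).
- Termination for a completer: Week 54 (Section 5.4).
- Visit window for Cycles 2-4: ±3 days (Table 7).
- Dosing interruption: return to therapy within 3 weeks (Section 6.7.4).
- Convention: Day 1 is the first dose and Week *n* covers Days 7*n* − 6 to 7*n*. This agrees with Table 7, which places Cycle 4 in Weeks 10-12.

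**On schedule**
- Dose 4: 21 × 3 + 1 = Day 64.
- Routine window closes: 64 + 90 = Day 154 = 22 × 7, the last day of Week 22.
- Week 54: Days 372 to 378.
- Interval: 372 − 154 = 218 days (31.1 weeks) to 378 − 154 = 224 days (32.0 weeks).
- Share of the Core study in time: 31.1/54 = 58%.

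**Scheduled visits**

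| Visit | First day of week | Days after Day 154 |
|---|---|---|
| Week 18 | 120 | −34 (inside the window) |
| Week 27 | 183 | 29 |
| Week 36 | 246 | 92 |
| Week 45 | 309 | 155 |

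Three of the four follow-up visits fall wholly between the two rules.

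**Sensitivity**
- Dose 4 at ±3 days (Day 61 or 67): the window closes on Day 151 or 157, in Week 22 or 23.
- One 3-week interruption, Termination still at Week 54: dose 4 on Day 85, close on Day 175, interval 197 to 203 days (28.1 to 29.0 weeks).
- All three dosing intervals each 3 weeks longer, Termination still at Week 54: dose 4 on Day 64 + 63 = 127, close on Day 217, interval 155 to 161 days (22.1 to 23.0 weeks).
- New anti-cancer therapy before Day 154 closes routine recording earlier and lengthens the interval.
- ET visit within 90 days of the last dose: no gap, provided new therapy has not already closed the routine window.

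**Which event is affected.** The late rule in Section 7.2.2 turns on when the investigator learns of the event, and that in Section 7.2 on when it is newly reported. Neither turns on onset. For an on-schedule completer:
- Related SAE at Week 30, learned of at Week 30: outside both dated rules.
- Related SAE at Week 30, learned of after Week 54: reportable immediately.

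**Part 1 against Part 2.** Table 6 marks adverse event review at Weeks 18-45 and at Termination with no 90-day footnote. Table 7 carries footnote 24. The visit lists in the text state the limit without separating the parts, so the Part 1 schedule and the text do not match.

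**The case against.** The strongest reply is that no gap in duty exists. Section 7.2.2 asks for any SAE within 24 hours, Section 7.2.5.1 ties the initial form to the investigator's knowledge without an end date, Section 4.6 has similar wording, and Section 7.2.4 allows no exceptions. An investigator who learns of a related SAE at Week 30 could reasonably feel bound to report it. This stands in part. A reader might infer that no SAE rule applies from Week 22 to Week 54, and the documents do not support that. But these clauses set the speed of reporting, not the period, and they conflict with a 90-day limit repeated throughout the protocol. If all SAEs were reportable without limit, the additional late rule would be largely unnecessary.

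A reader might also infer that every related SAE with onset in the interval is lost. That is too strong: one first learned of after Termination is covered. Nor are all subjects exposed.

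Sections 5.5 and 7.2 might be read as flatly contradictory on recording. They are not quite. Section 5.5 concerns eCRF entry, while Section 7.2 asks for recording and reporting to the sponsor without naming the eCRF, so a form sent to the sponsor could satisfy both. They still need to be reconciled.

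Finally, Section 7.2.1 refers to a Safety Manual for overdose reporting. If that manual also holds SAE instructions, sites may have clearer guidance than the protocol gives. This cannot be checked here and would not cure the protocol text.

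**Conclusion.** The point holds as a misaligned rule. For an on-schedule completer, about 31-32 weeks separate the end of routine SAE recording from the start of the explicit related-SAE duty, or about 28-29 weeks after one 3-week interruption. In that time a related SAE that arises after day 90 and becomes known before Termination is outside the recording window, and whether it must be reported is ambiguous.

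The size rests on nominal 3-week cycles, four doses and Termination at Week 54. It describes time, not subjects or events. The documents give no basis for estimating how many subjects would remain in the Core study beyond day 90, or how many such events would occur. A reader might infer that these events will be missing from the Safety Committee's reviews, or that the loss falls on the subjects with the most lasting immune effect. The documents establish neither: the committee is charged with all safety data and includes the sponsor's Medical Monitor, who receives the SAE forms. What can be said is that capture depends on how each site resolves a conflict in the text. In a first-in-human study with safety as the primary objective, the text should be corrected.

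**What to change.** 1. In Sections 7.2 and 7.2.2, start the related-SAE duty when routine recording ends: 90 days after the last dose, or the start of new anti-cancer therapy if sooner. Keep the 5-year end.
2. Add the same related-SAE exception wherever the 90-day limit is stated: the synopsis, Sections 3.1.1, 5.5, 5.8.1, 7.1 and 8.3, the Week 18-45 visit list, the Termination/ET list in Section 5.4, and Table 7 footnote 24. Otherwise an unqualified cut-off would remain in these places.
3. Reconcile Section 5.5 with Section 7.2 so that late related SAEs are recorded in the study safety data.
4. Bring the adverse event row of Table 6 into line with the text and Table 7.

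The cost is protocol wording and eCRF guidance, plus a few more SAE reports. No new visit is needed, because AE recording is already scheduled at Weeks 18, 27, 36, 45 and 54.
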